9.3.1 AE Follow up

All AEs occurring during the study are to be followed up in accordance with good medical practice until they are resolved, stabilized or judged no longer clinically significant or, if a chronic condition, until fully characterized. Any AEs that are considered drug-related (possibly related, definitely related) must be followed for 30 days, or to resolution, or until no improvement is expected, whichever occurs first.

9.3.2 Overdose

No information on treatment of overdose of Ampion is currently available. However, it is common medical practice to administer 5% HSA, the sole starting material of Ampion, in multiple infusions until hemorrhage is controlled thereby resulting in higher systemic concentrations of the significant components of Ampion.

In the case of overdose, the subject should be followed as for an AE and appropriate supportive medical treatment instigated.

9.4 SERIOUS ADVERSE EVENT REPORTING

9.4.1 Reporting Requirements

Unexpected serious suspected adverse reactions are subject to expedited reporting to FDA. ALL SAEs must be entered into the eCRF within 24 hours of first knowledge of the event by study personnel. It is important that the investigator provide his/her assessment of relationship to study drug at the time of the initial report. Entry of an SAE into the eCRF triggers an automatic alert to the CRO safety team. The following information must be reported:

- Protocol number
- Site and/or Investigator number
- Subject number
- Demographic data
- Brief description of the event
- Onset date and time
- Resolution date and time, if the event resolved
- Current status, if event not yet resolved
- Any concomitant treatment and medication
- Investigator's assessment of whether the SAE was related to Investigative product or not.

The CRO Safety Associate will contact the site for clarification of data entered onto the eCRF, or to obtain missing information. In the event of questions regarding SAE reporting, the site may contact the appropriate individual as in Section 9.4.2.

9.4.2 SAE Information

Ampio Pharmaceuticals Inc., or their designee CRO, is responsible for submitting reports of AEs associated with the use of the drug that are both serious and unexpected to FDA according to 21 CFR 312.32 and the final guidance (2012). All investigators participating in ongoing clinical studies with the study medication will receive copies of these reports for prompt submission to their Institutional Review Board (IRB) or Ethics committee (EC).

10 STATISTICAL METHODS

10.1 GENERAL CONSIDERATIONS

This section describes the rules and conventions to be used in the presentation and analysis of the data. A comprehensive presentation of the data management and statistical analysis plan will be approved by Ampio Pharmaceuticals, Inc., prior to study completion.

10.1.1 Statistical and Analytical Plan:

This is a randomized, confirmatory study in subjects with severe OA (KL 4) of the knee. Subjects will be followed over a 12-week treatment period to assess the efficacy of Ampion™ on changes in pain, stiffness and function, and patient satisfaction (PGA) and to assess the safety of Ampion™ by monitoring adverse events.

A within-patient, multi-component endpoint, OMERACT-OARSI responder analysis, evaluating pain, function, and PGA, will be used as primary analysis for this study.

The saline group in this study is designed to maintain a blind the study is not powered to make inference about patients receiving saline; therefore, the results from patients receiving saline will be summarized but no comparisons or inferences will be made.

10.2 STATISTICAL OBJECTIVES

The primary statistical objective is to evaluate the efficacy of a single intra-articular injection of Ampion. Efficacy will be evaluated by the percentage of patients who are considered an OMERACT-OARSI responder at 12 weeks after a single 4 mL Ampion™ intra-articular injection at Baseline.

OMERACT-OARSI response is evaluated by:

A patient in this study will be considered a responder for the purpose of efficacy analysis if the following criteria is met.

- 1) The patient has:
 - a. a percent improvement in pain (WOMAC pain) from baseline of $\geq 50\%$ and an absolute change in pain from baseline of ≥ 1 point; or
 - b. a percent improvement in function (WOMAC function) from baseline of $\geq 50\%$ and an absolute change in function from baseline of ≥ 1 point.

Meeting one of the above criterion designates the patient as a responder. If the patient does not meet this criterion, then the patient must meet the criterion below to be considered a responder.

- 2) The patient demonstrates improvement in at least 2 of the following:
 - a. Improvement in pain (WOMAC pain) over baseline of $\geq 20\%$ and a 0.5-point absolute change in pain

- b. Improvement in function (WOMAC function) over baseline of $\geq 20\%$ and a 0.5-point absolute change in function
- c. Improvement in patient global assessment (PGA) over baseline of $\geq 20\%$ and a 0.5-point absolute change in PGA

The second statistical objectives are to:

- Evaluate the improvement in the composite endpoint of pain and function (WOMAC A and WOMAC C) from Baseline to Week 12
- Evaluate the improvement in patient global assessment (PGA) from Baseline to Week 12
- Evaluate improvement in the composite endpoint of pain and function (WOMAC A and C) compared to saline from all single-injection Ampion studies.

The composite endpoint of pain and function (WOMAC A and WOMAC C) will be evaluated using a “controlled” OMERACT-OARSI responder criteria, defined as:

- Improvement in pain and function (WOMAC A and WOMAC C) over baseline of $\geq 20\%$ and a 0.5 point absolute change

Improvement in patient global assessment will also follow OARSI’s recommendation for a clinically meaningful improvement, defined as:

- Improvement in patient global assessment (PGA) over baseline of $\geq 20\%$ and a 0.5 point absolute change in PGA

10.3 ANALYSIS POPULATIONS

10.3.1 Safety Analysis Population:

The safety analysis population is defined as all subjects who receive study medication (Ampion or saline). Subjects will be analyzed as treated.

10.3.2 Intent-to-treat Population:

The intent-to-treat (ITT) analysis population is defined as all subjects who are randomized, regardless of whether or not they have received the investigational product, or have a post-baseline visit. All efficacy analyses will be performed in the ITT population. Subjects will be analyzed as treated.

10.3.3 Per Protocol Population:

The per protocol analysis population is defined as all subjects included in the ITT analysis who met all entry criteria, completed the Week 12 visit, and had no major protocol violations. All efficacy analyses will be repeated in the per-protocol population. These analyses will be supportive of the ITT analysis. Subjects will be analyzed as treated.

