8 TREATMENT

Eligible subjects will be randomized (6:1) to a single 4 mL Ampion intra-articular injection or a single 4 mL saline injection into the study knee.

Subjects will be randomized to an assigned subject number after confirmation of eligibility, just prior to treatment.

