2.3 Study Design

This is a randomized, double-blind study with a 7-day screening period for each patient followed by a 12-week participation period. A total of 171 subjects with osteoarthritis of the knee (OAK) will be randomized 6:1 across 2 study arms, 4 mL Ampion™ and 4 mL saline. Deferred treatment of pain in the most severe form of the disease is unacceptable to both patients and physicians, and a larger saline arm is not possible or necessary for true comparator purposes in severe OAK subjects. The saline arm is for control of unintended bias and is not intended for analysis; only the active Ampion arm will be analyzed for efficacy.

Severe OAK is a painful, incurable, and progressive disease with a highly predictable outcome. Methodological challenges exist in this debilitated patient population where an unmet medical need exists and there is no valid, licensed or approved control or therapy for severe OAK patients. Therefore, in addition to the 6:1 randomization that is in place to eliminate any unintended bias, the study plan will assess a historic control using all the severe OAK saline-treated patients from all previously completed, randomized, saline-controlled, single-injection Ampion studies. The historic control for this clinical trial has a similar demographic and concomitant treatment profile to the current study, which

allows an effective comparison. Analysis of Ampion and its comparison to this historic saline-control group will ensure a meaningful comparison and quantitative assessment of Ampion effect, in addition to the demonstration of an effect of at least some minimum size, which is considered essential for acceptance of efficacy, specifically in cases where the active control is not a licensed product (e.g. some vaccine trials, IGIV trials, etc.).

The clinical effects of treatment on OAK pain will be evaluated during clinic visits at 6 and 12 weeks, and telephone contacts at 2, and 10 weeks, using the Western Ontario and McMaster Universities Arthritis Index (WOMAC[®]) osteoarthritis Index 3.1 and the Patient's Global Assessment of disease severity (PGA).

The WOMAC[®] is a validated scoring system and sets the standard for the patient response. In order not to bias the collection of data, only questions from the validated WOMAC scale will be asked of subjects.

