4.10 MISSING DATA

All data collected under this study protocol will be included in the assessment of subject safety. Missing or incomplete AE data will assume greatest relationship to study drug and/or severity.

For the primary effectiveness endpoints (WOMAC A, WOMAC C, and PGA), missing Week 12 values will be imputed when the ITT analysis population is used. The Worst Observation Carried Forward (WOCF) will be selected as the primary method of imputing missing 12 Week data. Alternate imputation methods employed will include multiple imputations (SAS PROC MI and SAS PROC MIANALYZE) and Last Observation Carried Forward (LOCF). These sensitivity analyses will be conducted for the primary effectiveness endpoint, to ensure that the primary method of imputation chosen is robust with respect to imputation method

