7. LIST OF PLANNED TABLES, FIGURES, AND LISTINGS

Tables are categorized and numbered in accordance with ICH E3 guidelines. Each table, figure and listing is presented by treatment arm. All efficacy tables will be provided both for ITT and PP. Accountability tables will also include an overall column. Listings will be sorted by treatment, subject ID, and by visit, if multiple visits exist. These will be provided in a separate document.

| Number | Title |
|----------------------------|--|
| 14.1 Accountability | |
| 14.1.1 | Accountability (Analysis Population: All Enrolled) |
| 14.1.2 | Enrollment by Site (Analysis Population: All Enrolled) |
| 14.1.3 | Analysis Populations (include ITT, safety, PP, and reasons for PP exclusion) |
| 14.1.4 | Subject Disposition (all screened) |
| 14.1.5 | Major Protocol Deviations (Analysis Population: All Enrolled) |
| 14.1.6.1 | Demographics and Baseline Characteristics (Analysis Population: ITT) |
| 14.1.6.2 | Demographics and Baseline Characteristics (Analysis Population: PP) |
| 14.2 Efficacy | |

| Number | Title |
|--------------------|--|
| 14.2.1.1 | Summary of OMERACT-OARSI Percent Responder Status (Analysis Population: ITT) |
| 14.2.1.2 | Summary of OMERACT-OARSI “Controlled” Responders (WOMAC A and C) |
| 14.2.1.3 | Summary of Responders Demonstrating a 20% Improvement and 0.5 Shift in PGA |
| 14.2.1.4 | Summary of OMERACT-OARSI “Controlled” Responders (WOMAC A and C) Compared to Historic Saline |
| 14.2.1.5 | Summary of OMERACT-OARSI Percent Responder Status for a 50% Threshold |
| 14.2.1.6 | Summary of Patients Responding to 50% Improvement in Pain and 1.0 Absolute Change |
| 14.2.1.7 | Summary of Patients Responding to a 50% Improvement in Function and 1.0 Absolute Change |
| 14.2.1.8 | Summary of Patients Responding to a 20% Improvement in Pain and 0.5 Absolute Change |
| 14.2.1.9 | Summary of Patients responding to a 20% Improvement in Function and 0.5 Absolute Change |
| 14.2.1.10 | Summary of Patients responding to a 20% Improvement in PGA and 0.5 Absolute Change |
| 14.2.1.11 | Summary of WOMAC A mean change |
| 14.2.1.12 | Summary of WOMAC A percent change |
| 14.2.1.13 | Summary of WOMAC B mean change |
| 14.2.1.14 | Summary of WOMAC B percent change |
| 14.2.1.15 | Summary of WOMAC C mean change |
| 14.2.1.16 | Summary of WOMAC C percent change |
| 14.2.1.17 | Summary of WOMAC A and C mean change |
| 14.2.1.18 | Summary of WOMAC A and C percent change |
| 14.2.1.19 | Summary of PGA mean change |

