9. HANDLING OF MISSING OR INCOMPLETE DATES FOR ADVERSE EVENTS AND CONCOMITANT MEDICATIONS

9.1 Imputation Rules for Partial or Missing Stop Dates

If the month and year are present, impute the last day of the month. If only the year is present, impute December 31 of that year. If the stop date is entirely missing, assume the event or medication is ongoing. If a partial or complete stop date is present and the 'ongoing' or 'continuing' box is checked, then it will be assumed that the AE or concomitant medication stopped and the stop date will be imputed, if partial.

| | | Stop Date | | | | | | |
|-----------------|-------------------------------|-----------------------|-----------------------|------------------------------|------------------------------|----------------------------|----------------------------|---------|
| | | Complete: yyyymmdd | | Partial: yyyymm | | Partial: yyyy | | Missing |
| Start Date | | <1 st Dose | ≥1 st Dose | <1 st Dose yyyymm | ≥1 st Dose yyyymm | <1 st Dose yyyy | ≥1 st Dose yyyy | |
| Partial: yyyymm | =1 st Dose yyyymm | 2 | 1 | 2 | 1 | N/A | 1 | 1 |
| | ≠ 1 st Dose yyyymm | | 2 | | 2 | 2 | 2 | 2 |
| Partial: yyyy | =1 st Dose yyyy | 3 | 1 | 3 | 1 | N/A | 1 | 1 |
| | ≠ 1 st Dose yyyy | | 3 | | 3 | 3 | 3 | 3 |
| Missing | | 4 | 1 | 4 | 1 | 4 | 1 | 1 |

- 1 = Impute the date of first dose
- 2 = Impute the first of the month
- 3 = Impute January 1 of the year
- 4 = Impute January 1 of the stop year

Note: For subjects who were never treated (first dose date is missing), partial start dates will be set to the first day of the partial month.

Note: If the start date imputation leads to a start date that is after the stop date, then do not impute the start date.

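### The ITT set takes in every randomised subject but is analysed as treated, so the plan does not say whether an uninjected Ampion-randomised patient counts in n for the primary test

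*Protocol*

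**What the plan says.** Protocol 10.3.2 defines the ITT population as "all subjects who are randomized, regardless of whether or not they have received the investigational product, or have a post-baseline visit". It then sets the analysis rule: "All efficacy analyses will be performed in the ITT population. Subjects will be analyzed as treated". The same as-treated rule closes the definitions of the safety population (10.3.1) and the per-protocol population (10.3.3).

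The primary analysis (Protocol 10.3.4, SAP 4.1) is a one-sided exact binomial test of the responder proportion against 30% at alpha 0.025. SAP 2.3 restricts it to one arm: "only the active Ampion arm will be analyzed for efficacy".

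The SAP has no section defining the analysis populations. It uses the labels in its table plan (SAP 7: "All efficacy tables will be provided both for ITT and PP") and in its imputation rule (SAP 4.10: "missing Week 12 values will be imputed when the ITT analysis population is used", with worst observation carried forward, WOCF, as the primary method). It gives no rule for assigning ITT subjects to an arm. It mentions untreated subjects once, in a note on partial start dates in SAP 9.1: "For subjects who were never treated (first dose date is missing)".

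**The concern.** In the safety population, as-treated grouping is coherent, because everyone there received study medication. In the ITT population it is not. A patient randomised to Ampion and never injected has no treatment received and hence no arm. Since the efficacy test uses only the Ampion arm, there are two readings: the patient stays in n (arm as randomised) or falls out of n (arm as treated).

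The same rule has a second effect, and here the text is clear but departs from ITT. A saline-randomised patient given Ampion by mistake would enter the Ampion proportion, and an Ampion-randomised patient given saline would leave it.

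With a single proportion tested against a fixed value, n is part of the test. Dropping uninjected non-responders can only raise the observed rate, and there is no concurrent comparison in which such exclusions could balance out. The first two secondary tests, and the Ampion side of the Fisher comparison with historic saline, inherit the same ambiguity.

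**Working it through.** **Do other sections settle the reading?**

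- For keeping the patient in n: the ITT definition admits subjects "regardless of whether or not they have received the investigational product, or have a post-baseline visit", and missing Week 12 values are imputed in ITT.
- For leaving the patient out: the as-treated sentence itself, and Protocol 10.2, which describes the primary endpoint as response 12 weeks after an Ampion injection. Baseline (Protocol 10.3.6, SAP 4.4) is also tied to the start of treatment, which an uninjected patient never reaches.

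Membership of ITT is explicit. The arm, and hence n, is not, and no section resolves it.

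**Inputs.** Null rate 30% and one-sided alpha 0.025 (Protocol 10.3.4). Alternative 45%, n = 146 and power above 90% (Protocol 10.3.7, SAP 2.4). Earlier KL 4 responder rate 58.6% (Protocol Table 1.5.3). The number k of uninjected Ampion-randomised patients is not in the documents and is assumed. They are taken as non-responders.

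**Formula.** p = P(X ≥ x | n, 0.30), with X binomial. The critical count is the smallest x with p ≤ 0.025.

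**The plan's own figure.** At n = 146:

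- x = 56 (38.4%): p = 0.0189, pass.
- x = 55 (37.7%): p = 0.0284, fail.

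The critical count is 56. Power = P(X ≥ 56 | 146, 0.45) = 95.6%, which agrees with the stated figure of more than 90%.

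**The two readings near the boundary.** If k patients are dropped, n = 146 − k. If they stay in as non-responders, n = 146 and 56 responders are still needed.

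| k | n if dropped | critical count if dropped | p at that count | counts whose verdict changes |
|---|---|---|---|---|
| 1 | 145 | 55 | 0.0248 | 55 |
| 2 | 144 | 55 | 0.0216 | 55 |
| 3 | 143 | 55 | 0.0187 | 55 |
| 5 | 141 | 54 | 0.0214 | 54, 55 |

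**Chance that the verdict depends on the reading, k = 1.** This is P(X = 55 | n = 145, true rate):

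- true rate 38%: 6.8%. This rate is an assumption placed almost on the critical proportion, so it is close to a worst case.
- true rate 45% (planned): 1.5%.
- true rate 58.6% (earlier studies): 2.5 × 10⁻⁷, that is, below 0.0001%.

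**Away from the boundary.** The planned 45% corresponds to about 66 responders (0.45 × 146 = 65.7). With 66 responders, p = 0.000075 on n = 146 and 0.000034 on n = 143, so the conclusion is the same.

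**Power if uninjected patients stay in n as non-responders.** P(X ≥ 56 | 146 − k, 0.45) is 94.9% for k = 1, 91.1% for k = 5 and 88.6% for k = 7.

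**The case against.** The best defence is that the text already favours one reading. The ITT definition expressly includes uninjected subjects and is named as the set for all efficacy analyses; dropping them from a one-arm test would leave that clause with no work to do. The as-treated sentence could then be read as governing only which product label a dosed subject carries. This has weight, but it does not close the question. The sentence is not limited to dosed subjects, the endpoint wording points the other way, and even on this reading mis-dosed subjects move between arms, which is not ITT.

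On imputation, WOCF is not restricted to post-baseline values. WOMAC and PGA are recorded at screening and again before injection, so the worst of these cannot show improvement and the patient would be a non-responder. That is a reasonable inference, but the plan should say so. The SAP 9.1 note concerns only adverse event and medication dates. It shows that the SAP allows for untreated subjects, not that anyone considered their place in the primary analysis. The SAP is also written for protocol version 1.3, so the protocol's definitions can be taken to carry over; what carries over includes the conflict.

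The practical argument stands. Subjects are randomised "after confirmation of eligibility, just prior to treatment" of a single injection at the same visit, so few uninjected patients are likely. The mis-dosing effect is not quantified here and could move the rate in either direction.

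**Conclusion.** The concern holds: the rule is wrong as written. As-treated grouping conflicts with the ITT definition in the same section, and it leaves the denominator of a one-arm confirmatory test open to two readings. The expected numerical effect is small. With one to three uninjected non-responders, only a count of exactly 55 changes the verdict; with five, counts of 54 and 55 do. Near the planned or previously observed rates the conclusion is very unlikely to depend on the reading. These sizes rest on an assumed number of uninjected patients and on treating them all as non-responders; an uninjected patient who is followed up could have observed Week 12 data. The correction should be made because a confirmatory test should have its denominator fixed before unblinding, not because the result is likely to turn on it.

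**What to change.** - In Protocol 10.3.2, change the grouping rule for ITT efficacy analyses from as treated to as randomised. Keep as-treated grouping for the safety population.
- Repeat the ITT definition and its grouping rule in the SAP.
- State in the SAP that Ampion-randomised patients with no injection and no post-baseline data remain in n as non-responders, with baseline carried forward. Add how an uninjected patient with observed Week 12 data is counted.

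The cost is one sentence in the protocol and a short definition in the SAP, with no new data or patients. The reported responder rate may be slightly lower than under the lenient reading.

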AP-008	3	342	0 / 114 / 228	Multiple IA injection; 3 injections, every 2 weeks	WOMAC A pain, 5-point Likert scale	Week 20	WOMAC B WOMAC C PGA Physical activity WOMAC A pain with movement	Ampion, 4 mL
AIK	1 / 2	103	33 / 69 / 1	Single IA injection	Pain, 10-point NRS	Day 3, 8, 30 and 84	WOMAC total, parts A, B, C Range in motion Rescue analgesia	Ampion 10 ml, alone or in solution with betamethasone and/or lidocaine and/or saline
Total		1839						

*Both doses of Ampion, 4 mL and 10 mL, are safe, efficacious and well tolerated. In the absence of a difference in efficacy for the 4 mL and 10 mL Ampion doses, the lower dose of 4 mL will be used for subsequent phase 3 studies.

In all three well-controlled, single-injection studies, Ampion demonstrated a numerically greater effect in the KL 4 patients compared to saline, indicating a reproducible and consistent response. Analysis of the combined data demonstrate a statistically significant

[figure not shown]
result in this underserved patient population. Table 1.5.2 presents the data for KL 4 patients from all single-injection studies, analyzed according to the SAP for the respective study.

Table 1.5.2
Descriptive Statistics and Analysis Results for KL 4 Subjects for Each Study and All Studies Combined

Study ID	Parameter	Saline	Ampion	Unadjusted Diff. (Ampion-Saline)	LS Adjusted Diff. (Ampion-Saline)
Combined	N	223	194		
	Mean	-0.62	-0.82	-0.21	-0.19
	Std. Dev.	0.883	0.817		
	p-value			0.0125	0.0155
AP-003-A	N	43	32		
	Mean	-0.51	-0.86	-0.35	-0.42
	Std. Dev.	0.906	0.772		
	p-value			0.0774	0.0164
AP-003-B	N	67	65		
	Mean	-0.62	-0.81	-0.19	-0.14
	Std. Dev.	0.926	0.842		
	p-value			0.2197	0.3516
AP-004	N	113	97		
	Mean	-0.65	-0.82	-0.17	-0.15
	Std. Dev.	0.851	0.823		
	p-value			0.1440	0.1765

Figure 1 visually represents the consistent reduction in pain for Ampion-treated patients over a 12-week period.

Figure 1.
LS Mean Change for Ampion-Treated Patients Over Time and by Study

In accordance with FDA guidance on osteoarthritis, responder analysis according to the OMERACT-OARSI criteria was applied to previously conducted clinical trials, [Table 1.5.3](#).

Table 1.5.3
Responder analysis in KL 4 patients across single injection studies using OMERACT-OARSI criteria

Study ID	Ampion Responder (%)
AP-003-A	59.4%
AP-003-B	59.7%
AP-004	57.7%
Combined	58.6%

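### The supportive per-protocol run of the only saline test filters the Ampion patients but defines no matching filter for the historic saline patients

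*Protocol*

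**What the plan says.** Protocol 10.3.2 defines the ITT set as "all subjects who are randomized, regardless of whether or not they have received the investigational product, or have a post-baseline visit". Section 10.3.3 takes the per-protocol (PP) set from it: "all subjects included in the ITT analysis who met all entry criteria, completed the Week 12 visit, and had no major protocol violations". Both sets therefore consist of people randomized in AP-003-C.

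The same section states "All efficacy analyses will be repeated in the per-protocol population" and gives the role of that rerun: "These analyses will be supportive of the ITT analysis". SAP section 7 adds "All efficacy tables will be provided both for ITT and PP". Table 14.2.1.4, controlled responders on WOMAC A and C against historic saline, is on that list and is not exempted.

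The comparator is set in SAP 2.3 as a "historic control using all the severe OAK saline-treated patients from all previously completed, randomized, saline-controlled, single-injection Ampion studies". SAP 4.2 likewise refers to all the earlier saline arms, and tests the Ampion rate against them with Fisher's exact test. Neither document defines a PP set, a completion rule or a violation rule for the historic patients. Protocol 10.1.1 rules out any comparison with the concurrent saline arm, so this is the only test of Ampion against saline.

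**The concern.** Taken together, these sections put a filter on one side of a two-group comparison. Ampion patients who drop out, fail an entry criterion or have a major violation leave the PP table. Historic saline patients of the same kinds stay in.

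The likely direction can be read from the missing-data rule. In ITT, missing Week 12 scores are filled by worst observation carried forward (Protocol 10.4, SAP 4.10), which tends to make a dropout a non-responder. The PP set requires Week 12 completion, so it removes those patients from the Ampion denominator only.

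What is at stake is how the supportive analysis is read. A PP result that agrees with ITT is normally taken as reassurance. Here part of any PP advantage could come from selection, and a reader of the table could not separate that part out.

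**Working it through.** **The plan's own figure.** Protocol 10.3.7 and SAP 2.4 claim more than 90% power with 146 Ampion patients, 30% against 45%, one-sided 2.5%. The exact binomial rule rejects at 56 or more responders of 146. Its type I error is 0.0189 and its power 0.956, so the claim is correct and is not in question here.

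**Inputs from the documents.**
- Ampion: 146 (Protocol 10.3.7).
- Historic KL 4 saline: 223, from Protocol Table 1.5.2 ("Combined N 223 194"; 43 + 67 + 113 = 223).
- Test: Fisher's exact, alternative that Ampion is higher, one-sided level 2.5% (Protocol 10.3.4, SAP 4.2).

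**Assumptions, because the documents do not give them.**
- p: true controlled-response rate, set equal in both groups, 0.40 or 0.50.
- e: share of Ampion patients removed from PP, 10% in the main case.
- q: response rate of those removed, from zero to 125% of p.
- The historic group stays at all 223.

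**Formulas.** The Ampion PP size is 146(1 − e); with e = 0.10 that is 131.4, taken as 131. The Ampion PP response rate is (p − eq)/(1 − e). The chance of a significant result is the sum of the two binomial probabilities over every pair of counts with one-sided Fisher p ≤ 0.025.

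**Example.** With p = 0.40, e = 0.10 and q = 0, the Ampion PP rate is 0.40/0.90 = 0.444 against 0.40 for saline. With q = 0.20 it is (0.40 − 0.02)/0.90 = 0.422.

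**Results with no true difference and 10% removed.**

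| Response of those removed | Ampion PP rate, p = 0.40 | Chance of significance | Ampion PP rate, p = 0.50 | Chance of significance |
|---|---|---|---|---|
| 125% of average | 0.389 | 1.1% | 0.486 | 1.0% |
| Average | 0.400 | 1.9% | 0.500 | 1.9% |
| 75% of average | 0.411 | 3.1% | 0.514 | 3.4% |
| Half the average | 0.422 | 4.9% | 0.528 | 5.8% |
| None respond | 0.444 | 10.6% | 0.556 | 14.4% |

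The reference value, all 146 against all 223, is 1.9-2.0%.

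**Varying the share removed, none of them responding.** The chance is 4.8-5.7% at 5% removed and 21.3-31.3% at 15%.

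**How much removal turns a null result.** Take 66/146 (45.2%) against 100/223 (44.8%): one-sided p = 0.515. Removing 30 Ampion non-responders (30/146 = 20.5%) gives 66/116 (56.9%) against 100/223, p = 0.023. Across response rates of 30% to 60%, the share of non-responders that must go before near-identical ITT rates become significant falls from 28% to 16%.

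**Check of the remedy.** Removing the same share of non-responders from both groups (response 30-50%, 10-25% removed) gives 1.8-2.0%, so the level is held.

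**The case against.** The strongest objection is that no sentence says the historic group stays unfiltered in the PP table. The word 'all' in SAP 2.3 may describe only where the controls come from, and the earlier studies may have PP sets of their own that are not shown here. It is true that the asymmetry is inferred, from that wording plus the absence of any historic PP definition. But a programmer working from these documents has no rule for filtering the historic patients, and that gap has to be closed under either reading.

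A reader might also infer that the PP comparison is biased toward Ampion by construction. The documents do not support that. PP also removes entry failures and major violators, who may have observed Week 12 scores. Someone who took a prohibited analgesic could be a responder, and removing that patient lowers the Ampion rate. Worst observation carried forward makes non-response likely in dropouts without guaranteeing it. If those removed respond at the average rate there is no inflation. The 10.6-14.4% range is the extreme case.

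A further tempting reading is that the trial's error rate is inflated. It is not. PP is supportive, and the hierarchy rests on ITT. The percentages above are the chance that the PP run is significant taken alone, not the chance that ITT and PP are both falsely significant. A significant PP result cannot rescue a failed ITT test.

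Finally, Table 14.1.3 and Listing 16.5 will show PP exclusions in this trial. That helps, but neither shows how many historic patients a like rule would have removed.

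**Conclusion.** The point holds as an asymmetry in a supportive analysis. As written, the PP version of Table 14.2.1.4 compares Ampion patients who passed three filters with historic saline patients for whom none is defined. Because completion is required on one side only, the likely direction favours Ampion, but the documents do not fix the sign.

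The size depends on the share removed and on how those patients respond, both of which are assumed. At 10% removed it runs from slightly conservative, through no effect, to roughly two and a half to three times the 1.9-2.0% reference at half-average response, and higher in the extreme case. The confirmatory ITT test of the third secondary endpoint is untouched by this selection. The issue deserves correction because this is the only saline comparison in the plan and the remedy costs almost nothing.

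**What to change.** In SAP 4.2 and section 7, choose one of the following.

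1. State that the historic-saline comparison is run in ITT only, and exempt Table 14.2.1.4 from the PP repeat. Protocol 10.3.3 needs the same exception.
2. Define, before unblinding, a matching PP set for the historic saline patients: completed Week 12, met their own study's entry criteria, and had no major violation. Report the numbers removed from both groups, by reason, beside the result.

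The second option balances the selection step. It does not make the eligibility rules of the earlier studies equal to those of AP-003-C, and the SAP should say so. Setting the filter after unblinding would leave the choice open to the charge that it followed the data.

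The cost is a wording change plus either one table fewer or a filter on data already held. The PP result may come out less favourable to Ampion.
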